## **C. Exploratory**

Microbubble contrast-enhanced 2-dimentional transthoracic echocardiography (2D-TTE) results:

- Ejection fraction (LVEF)
- Multiple 2 and 4-chamber left (LV) and right ventricular (RV) dimensions, including:
  - end systolic left ventricular volume (LVESV)
  - end diastolic left ventricular volume (LVEDV)
  - left atrial area and volume
  - valvular insufficiency and/or gradients

Multiple calculated monitoring parameters using velocity and flow measurements entered by sites, including:

- Stroke volume (SV)
- Cardiac output (CO)
- Derived left ventricular filling pressure (E/e')

- LV Circumferential Shortening (CS)

Biomarker concentrations:

- Observed value and change from baseline in the following
  - Additional biomarkers: hsCRP, troponin-I and/or hs-troponin T, CPK, CPK-MB, and lactate dehydrogenase.
  - Exploratory biomarkers: NT-proBNP, total BNP

Plasma concentrations:

- Concentration-QT correlation performed on baseline-corrected QTcF time matched with PK.

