### 6.1 Study Treatment(s) Administered

**Table 5** Study Treatment Details

Study Treatmenta Name:	JK07 (recombinant fusion protein consisting of a fully human immunoglobulin G1 monoclonal antibody and an active polypeptide fragment of the human growth factor NRG-1)	JK07 matching placebo
Dosage Formulation:	Sterile solution	Sterile solution
Unit Dose Strength(s)/Dosage Level(s):	20 mg/mL JK07 in 2 mL of formulation buffer containing 25 mM histidine/histidine-HCl, 205 mM sucrose, 0.04 % (w/v) polysorbate 80, pH 6.0.	Formulation buffer (25 mM histidine/histidine-HCl, 205 mM sucrose, 0.04 % polysorbate-80, pH 6.0).
Route of Administration:	Intravenous (IV) infusion over 60 minutes using a syringe pump or infusion pump	IV infusion over 60 minutes using a syringe pump or infusion pump
Dosing Instructions:	Single dose per protocol treatment regimen	Single dose per protocol treatment regimen
Packaging and Labeling:	Study treatment will be provided in a single-use vial or vials. Each vial will be labeled as required per country requirement. JK07 will be provided with the appropriate infusion kits as part of the Clinical Trial Supplies.	JK07-matching placebo will be provided in the appropriate infusion kits as part of the Clinical Trial Supplies.
Manufacturer:	Emergent Camden	Emergent Camden
Prepared Solution Expiration:	JK07 infusions will be prepared at the study center for administration within 4 hours following the dose preparation.	Placebo infusions will be prepared at the study center for administration within 4 hours after dose preparation.

a With the exception of IP infusion administered to the sentinel subject in each cohort, all study staff will be blinded to IP identification

The infusion will be managed through a syringe pump or infusion pump. A needle or catheter between 16G and 21G is required by this protocol (choice as per Site procedures); needles narrower than 21G are NOT allowed. The total infusion time, inclusive of saline flush should be 60 minutes and should not exceed 75 minutes, and reasons to exceed this time must be reported. The infusion time should not be less than 60 minutes under any circumstance. The date/time of start and time of stop of the infusion, infusion rate, volume infused, any interruption, and stop/restart will be documented in the eCRF.

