### **8.2.9 Two-dimensional Transthoracic Echocardiography**

Left ventricular and hemodynamic performance indices measured by 2D-TTE will be explored. Potential effects of JK07 will be evaluated as change from baseline and will be compared with changes from baseline in subjects receiving placebo.

On Day 1, 2D-TTE will be performed locally following American Society of Echocardiography guidelines and recommendations, pre-dose and at 6 hours  $\pm$  30 minutes, and on Day 2 at 30 hours  $\pm$  30 minutes following completion of the dosing infusion, and at subsequent times described in the [Table 1](#) SoA.

The full examination will be evaluated locally for safety and will be digitally transferred to the Central Laboratory for centralized evaluation and centralized calculation of the measurements. Measurements taken by the Central Laboratory will include but are not limited to: ejection fraction, multiple LV chamber dimensions, including LVESV, LVEDV, as well as multiple calculated monitoring parameters using velocity and flow measurements including SV, CO, and E/e' calculations (Please see [Appendix 5](#) for detailed listing).

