## Appendix 5 2-D TTE Parameters

- LVIDs (mm)
- LVIDd (mm)
- LVIDd diameter/BSA (mm/m^2)
- LVIDd diameter/height (mm/m^2)
- Septal thickness (cm)
- Posterior Wall thickness (cm)
- Biplane MOD
- LVEDV (mls/m^2)
- LVESV (mls/m^2)
- LVSV (mls/m^2)
- LVEF (%)
- Circumferential Shortening (CS) + EDC-ESC/EDC
- Cardiac Output/Cardiac Index & Stroke Volume (LVOT VTI pulsed wave Doppler method)
- Diastolic Function Grade (E/A ratio, E/E' ratio)
- Mitral Valve Regurgitation Grade (Quantitative)
- Left Atrial Area and Volume
- Right Ventricular Size and Function
- Tricuspid Valve Regurgitation Velocity
- Peak Mitral Valve Regurgitant Velocity
- Left Ventricular Outflow Tract Doppler Time Velocity Integral

Abbreviations: BSA, body surface area; CS, circumferential shortening; E/A ratio, ratio of early (E) to late (A) ventricular filling velocity; EDC, end diastolic circumference; ESV, end systolic circumference; LV, left ventricular; LVEDV, left ventricular end-diastolic volume; LVESV, left ventricular end-systolic volume; LVEF, left ventricular ejection fraction; LVIDd, left ventricular internal end-diastolic diameter; LVIDs, left ventricular internal end-systolic diameter; LVOT left ventricular outflow tract; MOD, method of disks; SVR, systemic vascular resistance; VTI, ventricular time integral

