### **B. Purpose of the Statistical Analysis Plan**

This Statistical Analysis Plan (SAP) is based on the JK07.1.01 study Protocol Amendment 3.0, providing additional details concerning the statistical analyses outlined in the protocol and reflecting any changes to the protocol.

This SAP will govern the analysis of data from this study. This plan contains definitions of analysis populations, derived variables, data handling rules, format of data presentation and statistical methods for the safety, pharmacokinetic (PK), and pharmacodynamic (PD) analyses. The plan may be modified until the time of database lock. The database will be locked after medical/scientific review of the data has been completed, protocol deviations have been identified, and the data have been declared clean. The purpose of the SAP is to ensure the credibility of the study findings by pre-specified statistical approaches to the study data prior to the database lock. This plan will not repeat all the definitions given in the protocol but will provide further details of summaries and analyses planned therein. Any deviations from the analysis plan, including any after the time of database lock, will be documented as such in the study report. Table, Listing, and Figure (TLF) shells are provided in a separate, accompanying document. The SAP will take precedence over the protocol.

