### A. Analysis of 2-dimensional Transthoracic Echocardiography (2D-TTE) and Biomarkers

Same as the non-PK/PD analysis, the subjects who received placebo will be combined into one treatment group for purposes of analysis. The baseline measure will be defined as the last non-missing measure prior to initiation of IP. Change from baseline will be calculated as post baseline value subtracted by value at baseline. Exploratory inferential comparisons to placebo may also be performed.

Results of the 2D-TTE and biomarkers and their change from baseline values (as applicable) will be listed and descriptively summarized by treatment at scheduled time point (details are in the Protocol JK07.1.01 – Amendment 3 Section 1.3, Schedule of Activities) Summary statistics including n, min, max, mean, SD and median will be calculated.

Values outside of the laboratory's reference range (i.e., those with low or high values) will be flagged in the listings if applicable.

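### SAP III.C takes stroke volume, cardiac output, E/e' and circumferential shortening from site-entered measurements, although Protocol 8.2.9 assigns them to the Central Laboratory; the change is not declared

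*SAP*

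**What the plan says.** **Protocol.** Section 8.2.9 has each full echo examination read locally for safety, after which it "will be digitally transferred to the Central Laboratory for centralized evaluation and centralized calculation of the measurements". The measurements it assigns to the Central Laboratory include those from "velocity and flow measurements including SV, CO, and E/e' calculations", and it points to Appendix 5 for the full list. Appendix 5 contains "Circumferential Shortening (CS) + EDC-ESC/EDC". The same section states the purpose: changes from baseline on JK07 "will be compared with changes from baseline in subjects receiving placebo".

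**SAP.** Section III.C splits the echo endpoints into two groups. LVEF, LV and RV dimensions, ventricular volumes and left atrial size come first, with no source given. Stroke volume (SV), cardiac output (CO), E/e' and circumferential shortening (CS) follow under "Multiple calculated monitoring parameters using velocity and flow measurements entered by sites, including". Section IX.A then states: "Results of the 2D-TTE and biomarkers and their change from baseline values (as applicable) will be listed and descriptively summarized by treatment". It names no source for the values. Section I.B adds: "The SAP will take precedence over the protocol".

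**The concern.** For four echo variables the two documents name different sources, and the document that prevails names the one the protocol set aside for safety. The reference to sites is the SAP's own addition. The protocol's endpoint text (Synopsis and Table 3) describes the same velocity and flow parameters without saying who enters the measurements.

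The comparison of echo change from baseline with placebo, an exploratory objective, is at stake. If the programmers follow SAP III.C, the summaries of SV, CO, E/e' and CS use measurements made separately at each centre, although centrally standardised values of the same variables are planned. If they follow the protocol instead, they depart from the governing text. If the source stays unsettled, it can be chosen after results are seen, and pre-specification is meant to prevent that.

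**Working it through.** **1. Source of each variable**

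| Variable | Protocol 8.2.9 and Appendix 5 | SAP III.C |
|---|---|---|
| SV, CO, E/e' | Central Laboratory, named in 8.2.9 | Site-entered |
| CS | Central Laboratory, through Appendix 5 | Site-entered |
| LVEF, LVESV, LVEDV | Central Laboratory | No source given |
| Left atrial area and volume | Central Laboratory, through Appendix 5 | No source given |

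The conflict is confined to the first two rows. CS is not a flow measure: Appendix 5 defines it from end-diastolic and end-systolic circumferences. It belongs here only because the SAP lists it under the site-entered heading.

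**2. Whether the SAP corrects or declares the difference**

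- IX.A (echo analysis): no source named.
- V.A (Data Sources): eCRF data plus electronic transfers. The only transfer named is laboratory data; no central echo feed is listed.
- Changes from Protocol: covers abnormal vital signs only.
- I.B: the SAP prevails.

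**3. How the SAP treats other data with two sources**

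- ECG (VII.G): Central Reader and Principal Investigator results are displayed separately.
- Biomarkers (X): local and central results are summarised separately.
- Echo: no rule.

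**4. Scale of the groups**

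The plan's maximum reproduces: 7 cohorts × 9 subjects = 63, of whom 7 are sentinels and 56 are randomised. A base cohort randomises 3:1 and an expanded cohort 6:2, so pooled placebo runs from

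- 5 cohorts × 1 = 5 subjects, to
- 7 cohorts × 2 = 14 subjects.

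SAP V.E plans no centre adjustment. Assume 8 equal sites with placebo subjects falling at random. The expected number of sites with no placebo subject is then 8 × (7/8)^n:

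- n = 5: 8 × 0.513 = 4.1 sites
- n = 14: 8 × 0.154 = 1.2 sites

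Those sites offer no within-site comparison of JK07 with placebo.

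**5. What extra noise would do (illustration only)**

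Neither document gives an SD, an effect size or a power target. Assume two-sided 5%, 80% power and a normal approximation. The detectable difference between one dose group's randomised JK07 subjects and pooled placebo is then k × (1.960 + 0.842) × √(1/n₁ + 1/n₀), in units of the central-read SD. Here k is the factor by which local reading inflates the SD.

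| n₁ vs n₀ | k = 1.0 | k = 1.1 | k = 1.4 |
|---|---|---|---|
| 3 vs 5 | 2.05 | 2.25 | 2.86 |
| 6 vs 14 | 1.37 | 1.50 | 1.91 |

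The equivalent loss of information is 1 − 1/k²: 17% at k = 1.1 and 49% at k = 1.4. The range for k is an assumption with no support in the documents. The table shows only that groups this small have little room for avoidable noise.

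**The case against.** The strongest reply is that the heading in SAP III.C describes data entry. It does not say who calculates the parameters or that central values are discarded, and sites might even be transcribing central results. That stands as an ambiguity and does not remove the point. If sites supply the inputs, the measurements are local whoever does the calculation; if they transcribe central values, the SAP needs to say so.

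A second reply also has force. Apart from the sentinels, site staff are blinded: "With the exception of IP infusion administered to the sentinel subject in each cohort, all study staff will be blinded to IP identification". Change from baseline removes a constant reader offset when the same reader reads every visit. For randomised subjects, reader variation is therefore mostly noise. What remains is that noise, any change of reader between visits, and chance imbalance between unadjusted sites.

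A reader might infer more than the documents support:

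- **That LVEF and volumes are also taken from sites.** The site-entry heading does not cover them. SAP I.B says it does not restate every protocol definition, so where the SAP is silent Protocol 8.2.9 still applies.
- **That open-label sentinel scans bias the comparison.** SAP V.K limits the PD population to randomised subjects, and sentinels are not randomised (SAP IV.D). Protocol Table 11 is wider, but the SAP prevails.
- **That reader differences cannot be separated from drug effect at all.** Blinded reading and change from baseline make this too strong.
- **That there are eight sets of readers, or that central reading is masked to visit.** The documents give about 8 centres. They do not state the number of readers or the Central Laboratory's masking to visit.

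**Conclusion.** The point holds for SV, CO, E/e' and CS. The governing text contradicts Protocol 8.2.9 on their source, does not declare the change, and has no local-versus-central rule of the kind it applies to ECGs and biomarkers.

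The consequence is limited. These endpoints are exploratory, no formal hypothesis test is planned, inferential comparison with placebo is optional, and no primary or secondary endpoint is touched. The expected effect is extra measurement noise and possible site imbalance in very small groups, and the documents do not allow it to be sized. The conclusion rests on reading the SAP heading at face value and on its precedence clause; it does not depend on any assumed SD inflation. The correction is worth making because the central measurements are already planned.

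**What to change.** - **SAP III.C:** strike the attribution to site entry and state that the velocity and flow measurements, and CS, are measured by the Central Laboratory under Protocol 8.2.9.
- **SAP IX.A:** state that all 2D-TTE summaries and any placebo comparisons use Central Laboratory values. Show site-entered values separately, as a listing or a second summary, following the ECG and biomarker pattern.
- **If site values are really intended:** record the change and the reason for it in Changes from Protocol.

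The cost is SAP wording, a check of the table, listing and figure shells, and confirmation that the central echo data transfer is listed in SAP V.A. The images already go to the Central Laboratory, so no new reader or procedure is needed. The SAP can be modified until database lock.

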## IV. Study Design

### A. Design Overview

This is a phase 1, randomized, double blind, placebo-controlled, single ascending dose study to assess the safety, tolerability, immunogenicity, and pharmacokinetics (PK) of JK07 in subjects 18 to 80 years of age of chronic heart failure (HF) with reduced ejection fraction (HFrEF)  $\leq 40\%$ .

[figure not shown]
Initially 5 cohorts are planned with the option to expand the study to a total of 7 cohorts. The size of the cohorts will range from 5 to 9 subjects. Each cohort will include a single active unblinded sentinel subject receiving a single intravenous dose of JK07 prior to randomizing JK07 or placebo administration in the remaining of the cohort.

Approximately 8 investigators and study centers are expected to participate in this study. A maximum of 63 subjects will be enrolled into dose escalation cohorts. Five dose escalation cohorts are planned. Two additional cohorts may be added per the Data Review Committee (DRC) decision (total up to 7 cohorts). The details of the treatment design are in the protocol Amendment 2, section 4.1. In summary:

- For each dose level, the DRC will evaluate the sentinel subject's safety data for clinical effects and dose limiting adverse events (DLAEs) and decide whether to randomize and apply treatment to other subjects in this cohort at JK07: placebo = 3:1.
- When a clinical effect observed in a subject (sentinel subject or randomized subject), the DRC will decide whether to proceed with the trial in the cohort as planned, expand the cohort (up to a maximum of 9 subjects in total, i.e. 1 open-label JK07 sentinel subject, and 6:2 [JK07: placebo] randomized, double-blind subjects), stop the trial, or reduce the dose level.

- The DRC evaluates the safety data of all subjects in the evaluation period (at least 15 days and up to 180 days following the administration of the IP) and decides whether to proceed dose escalation.

The study schema is presented in [Figure 1](#).

**Figure 1 Study Schema**

The JK07 dose level of which are shown in [Table 1](#). The process above will proceed until the highest planned dose level (1.08 mg/kg) is reached or the DRC decides not to escalate dose further. Two additional higher cohorts may be added as per the DRC recommendation (total up to 7 cohorts with the highest JK07 dose administered not to exceed 2.5 mg/kg without further amending the protocol. DRC may decide to reduce the amount of dose in cohort 6 and cohort 7 based on the results of the previous cohorts. They may also decide to proceed with a cohort of decreased dose level (which may be pre-assigned dose level or not). Following a dose reduction, the DRC may

subsequently proceed with another cohort with reduced or increased dose level. A sentinel subject is required only if the selected dose level is above the previous Highest Confirmed Safe Dose (HCSD).

**Table 1 Dose Levels**

Cohort	Dose level of JK07
Cohort 1	0.03 mg/kg
Cohort 2	0.09 mg/kg
Cohort 3	0.27 mg/kg
Cohort 4	0.54 mg/kg
Cohort 5	1.08 mg/kg

Subjects' safety/tolerability data in at least the first 15 days of the study will be used for DRC's decision in whether to escalate to the next dose level. Preliminary PK results, and/or PD/biomarker results will also be taken into consideration if available and applicable. The DRC determines whether an AE observed after JK07 administration is DLAE and monitors DLAEs throughout the study. After Day 30, only SAEs deemed at least possibly related to the IP or study procedures will be captured and may be taken into consideration for dose escalation where applicable. In addition, subjects withdrawn due to an adverse event (AE) prior to the IP administration will be replaced.

## **B. Study Population**

Individuals eligible to participate in this study must meet the criteria listed in Sections 5.1 and 5.2 of the Protocol.

All relevant medical and non-medical conditions will be taken into consideration when the decision is made upon whether this Protocol is suitable for a subject. Eligibility criteria may not be waived.

Screen failures are defined as subjects who consent to participate in the clinical study but are not subsequently assigned to study treatment. A minimal set of screen failure information is required to ensure transparent reporting of screen failure subjects to meet the Consolidated Standards of Reporting Trials publishing requirements and to respond to queries from regulatory authorities. Minimal information includes demography, screen failure details, eligibility criteria, and any SAE.

### **C. Sample Size**

Approximately 8 investigators and study centers are expected to participate in this study. A maximum of 63 subjects will be enrolled in the dose escalation cohorts. Five dose cohorts are planned. Two additional cohorts may be added as per the Data Review Committee (DRC) recommendation (total up to 7 cohorts) to receive IP.

For this study, no prospective calculations of statistical power have been made. The sample size is not based on statistical considerations but is typical for studies of this nature and is considered adequate to characterize the distribution of the planned endpoints. Any statistical testing will be considered exploratory and descriptive.

### **D. Treatment Randomization**

Double blind randomization with placebo control is employed in this study to minimize bias. All subjects other than sentinel subjects will be centrally assigned to randomized study treatment using an Interactive Web Response System (IWRS). Before the study is initiated, the log in information & directions for the IWRS will be provided to each study center. Study treatment will be administered by the site.

For those subjects other than sentinel subjects, prior to randomization each subject will be assigned a unique number (randomization number) in ascending numerical order at each study center. The randomization number encodes the subject's assignment to either JK07 or placebo, according to the randomization schedule generated prior to the study by the Randomization Biostatistician at IQVIA Biotech. Each subject will be dispensed blinded study treatment, labeled with his/her unique randomization number on Day 1 of the study.

The details of randomization and unblinding plan and randomization schedule are documented separately.

Subjects will be randomized to study treatment at cohort level. After a sentinel patient is enrolled, each cohort will randomize 4 subjects in a 3:1 ratio to JK07 vs. Placebo. Subject stratification is not required.

## **V. General Analytical Considerations**

### **A. Data Sources**

Data are recorded on electronic Case Report Forms (eCRF), entered into the study's electronic data capture system (EDC), unless it is data that is being transmitted to the Sponsor or designee electronically. Laboratory Data will be transmitted to the Sponsor by Q Solutions.

Statistical analysis will be performed following IQVIA Biotech standard operating procedures and on the IQVIA Biotech computer network. All statistical analyses will be performed using SAS Version 9.4 with program code prepared specifically for the project by qualified IQVIA Biotech statisticians and SAS programmers.

### **B. Definition of Baseline**

This is a single-dose study. Unless otherwise specified, baseline is defined as the last non-missing measurement prior to study IP administration. Change from baseline will be calculated as post-baseline values minus baseline values.

